**Each sleep study night will consist of the following procedures:**

*Pre-sleep procedures.* Subjects will undergo a history and physical examination. They will report to the CRU at 4:00 PM and undergo anthropometric assessment including weight, height, neck, and waist circumference. At 5:30 PM, they will eat a standard dinner containing 30% fat, 50% carbohydrate, and 20% protein with kcal based upon the Mifflin-St Jeor formula. Two peripheral IVs (18 to 20 gauge) will be placed. All samples are obtained through the IV without disturbing the subject during sleep. Blood pressure will be checked at 6:30 PM, before administration of study drug. If systolic blood pressure is <90 or the heart rate is <50 then no drug will be administered. (In the event that this occurs, the study will still proceed so that CPAP and OSA nights can be compared and analyzed as a "no drug" group.) If blood pressure and heart rate are acceptable, propranolol LA 80 mg, or placebo (random order, crossover on study night 2 and 3) will be given. Participants and the investigators will be blinded to drug assignment.

*PSG setup.* On each study night from 10:30 PM until 6:30 AM, a PSG will be performed. The sleep study will include electroencephalography, electrooculography, oxygenation, respiratory effort, CPAP airflow, and transcutaneous CO2 monitoring. Respiratory effort will be measured by thoraco-abdominal movement assessed by mercury strain gauges. Surface electrodes will be placed at C3A2 and C3O1, a submental electrode, and left and right electro-oculogram will be used to stage sleep. Electrocardiograph (EKG) tracings will be recorded from three chest electrodes. Continuous measurement of oxygen saturation will be recorded using an ear oximeter (model No 472-1A, Hewlett Packard, Waltham, Mass). Transcutaneous CO2 will be monitored using a Radiometer TCM-4 device. Signals from the electroencephalograph, EKG, electromyogram, electrooculogram, respiratory strain gauge, ear oximeter and thermistors will be recorded on a computer with RemLogic software.

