and CPAP airflow. Therefore, we use a validated technique to quantify differences in FAO between studies by providing an oral liquid dose of 15 mg/kg body mass of [H31]palmitate taken with dinner. The isotope is dissolved in a warm (60 °C) liquid shake (such as Ensure®). The isotope is non-radioactive and synthetic (Cambridge Isotope Laboratories DLM-215-MPT). FAO will be quantified thereafter by hourly assessment of deuterium incorporation into plasma H2O using anisotope ratio MS (IR/MS). Subjects will also ingest 0.4 g/kg body mass of H2O (10% enriched; CIL OLM-240-10-0, Andover MA) to calculate total body water (TBW) by isotope dilution. The FAO rate will be determined by excess plasma H times TBW, while percent recovery of deuterium will be determined by dividing by dose of H administered. All tracers in this protocol are tested for microbiological contamination, and are exempt from FDA IND status (see email correspondence with FDA # PIND 132066). The isotopes of H O and [H31]palmitate are stored in the PI's laboratory. Their required amount is prepared for each participant and brought to the CRU. The [H31]palmitate is dissolved in an Ensure shake and heated in the kitchen by nursing staff or dietitian in CRU.

*Blood sampling and morning urine sample collection.* The first blood sample is taken at 5:30 PM, just before dinner and serves as a pre-medication, pre-isotope baseline. Subsequent samples are drawn hourly while the subject is awake. At 10:30 PM, when the sleep study starts, blood is sampled more frequently, at 30 minute intervals in order to capture dynamic changes in metabolism during sleep. Additional samples will be drawn towards the end of each palmitate infusion period, to ensure a plateau of isotope enrichment. Each blood sample will be 4 cc in volume and placed into lavender top tubes (EDTA) for centrifugation to obtain plasma. Cells are removed from plasma by centrifugation for 10 minutes at 1500 x using a refrigerated centrifuge. Following centrifugation, plasma will be transferred to cryovials for storage. In patients that have signed the optional consent for isolation of genetic material, we will collect an additional 16 cc (4 tubes) at 6:30 AM upon awakening since this volume is required for isolation of peripheral mononuclear cells. The final sample is obtained at 9:00 AM. .

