### Data Analysis and Anticipated Outcomes:

The primary outcomes are nocturnal glucose and FFA levels. The main independent variable is experimental condition: [CPAP], [OSA+placebo], or [OSA+propranolol]. Since glucose and FFA are measured multiple times per subject per night, we will perform mixed linear model analysis using condition as a fixed factor and subject ID as a random factor. We will also examine whether there are independent or interacting effects of time, or time x condition on trajectories of FFA and glucose. We hypothesize that OSA increases glucose and FFA levels during [OSA + placebo] nights, compared to [CPAP], or [OSA + placebo] nights. We further hypothesize that propranolol will suppress nocturnal FFA and glucose to levels similar to that of CPAP. Sleep physiology that is measured on a continuous basis will be condensed into 30 minute bins to create a parallel data structure with metabolic parameters. We will then examine whether sleep physiology (e.g. AHI, arousals, heart rate) is dynamically associated with glucose or FFA, and whether urine catecholamine levels are associated with increases in FFA or glucose. For variables measured once (RHI, morning lipid profile) or averaged together (e.g. nocturnal glucose level) we will perform one-way ANOVA for comparisons. We will also compare sleep physiology between the 3 nights, examining variables such as apnea hypopnea index, metrics of hypoxia, and sleep architecture/duration. A questionnaire will be administered each morning to assess subjective sleep quality from the night prior, and to screen for any symptoms related to study medication. These responses will be used to determine how symptomatic a subject's OSA is, whether subjective sleep quality correlates with extent of metabolic change, and whether any side effects of beta blockade were perceived.

Regarding tracer data, we predict that  $R_a$  FFA and  $R_a$  glycerol will exhibit a ~3:1 ratio reflecting typical patterns of lipolysis without significant intra-cellular recycling. Based on studies of normal sleep [39, 40], we predict that on CPAP, sleep reduces lipolysis and FAO compared to wakefulness. During CPAP withdrawal, sleep will increase lipolysis (or at least mitigate sleep-induced suppression) compared to wakefulness. We hypothesize that FAO will be reduced or unchanged by OSA. This pattern of increased lipolysis without increased FAO may lead to

ectopic lipid deposition and extracellular TG cycling (see figure).

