Stable isotopes [ $^2H_{31}$ ]palmitate and  $H_2^{18}O$  will be used to follow the fate of ingested fat (palmitate), and to quantify the plasma water pool size to permit calculation of tracer oxidation rate. This is a validated technique to quantify FAO by providing an oral liquid dose of [ $^2H_{31}$ ] palmitate taken with dinner [53]. We will administer [ $^2H_{31}$ ] palmitate orally with dinner in a liquid emulsion (such as an Ensure® shake) at a dose of  $15 \text{ mg/kg}$  body weight (approximately  $1.7 \text{ g}$  of fat for a  $120 \text{ kg}$  person, Cambridge Isotope Laboratories DLM-215-MPT). In addition, we will administer a stable isotope of water, [ $H_2^{18}O$ ] 10% orally at a dose of  $0.4 \text{ g/kg}$  body weight (about  $48 \text{ mL}$  for a  $120\text{-kg}$  person, Cambridge Isotope Laboratories OLM-240-10-0). When [ $^2H_{31}$ ]palmitate is oxidized, the  $^2H$  is released into the plasma  $^2H_2O$  and is quantified by mass spectroscopy.

**b. Justification and safety information if FDA approved drugs will be administered for non-FDA approved indications or if doses or routes of administration or participant populations are changed.**

We will be administering unmodified, marketed product via the typical oral route at a standard clinical dose. This proposal was presented the FDA and qualified as exempt from IND application (see separate documentation). Propranolol is FDA approved for indications including hypertension, migraine, supraventricular tachycardia, and essential tremor and lawfully marketed in the United States. This research is not intended to support any change in the advertising or labeling of the drug. A conventional starting dose of drug is being administered, and the drug will be administered one time during the study. The investigator will not represent the drug in any promotional context, distribute, test-market, or charge for the drug.

Propranolol is a non-selective (beta-1 and beta-2 receptor), non-vasodilating beta adrenergic receptor antagonist. It has been used for decades for hypertension and angina as well as "off label" for other

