**7. Study Statistics**

- a. Primary outcome variable: Nocturnal FFA and glucose profile
- b. Secondary outcome variables: Morning EndoPAT, lipid panel. Sleep study parameters (e.g. total sleep time, latency, wake after sleep onset, sleep stages, AHI, oximetry, heart rate). Lipid flux data (rate of lipolysis and FFA turnover using stable isotope data; rate of fatty acid oxidation), DNA methylation profile.
- c. Statistical plan including sample size justification and interim data analysis.

**Comparisons between CPAP, [NDS + propranolol], and [NDS + Placebo]:** Primary outcome is comparison of metabolism and blood pressure for [NDS + propranolol] versus [NDS + placebo]. For metabolic parameters that are repeatedly measured during sleep (e.g. FFA, glucose) we will use mixed linear model analysis with experimental group as a fixed factor and subject ID as a random factor. Sleep physiology that is measured on a continuous basis (e.g. heart rate, AHI, SpO2) will be condensed into 30 minute bins to create a parallel data structure with metabolic parameters. We will then examine whether these sleep physiological metrics are dynamically associated with glucose/FFA level. For those parameters that are measured once per visit (e.g. RHI, lipid panel), we will compare using paired T-tests for within-subject comparisons between nights. A secondary outcome is whether CPAP and [NDS + propranolol] are similar, and this will be performed using a similar pairwise comparison. In addition, one way ANOVA will be used to ascertain whether there is a detectable difference across all three groups. Multiple regression will be used to examine associations between FFA, glucose, CPAP status, and drug adjusting for potential confounders such as diabetes, BMI, body fat (DEXA) and age. As an exploratory analysis, Pearson correlation matrices will be used to probe the interrelatedness of glucose, FFA, insulin, lipids, and sleep outcomes, followed by targeted multivariable regression. We plan an analysis of each subject's pulse rate and blood pressure after their PSG to determine whether beta blocker dosage or timing requires adjustment, which will expedite the ability to tailor the therapy if necessary.

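### The protocol's fatty acid oxidation rate is a cumulative amount since dinner, so as written it cannot show the predicted fall in oxidation during sleep

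*Protocol*

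**What the plan says.** Protocol section 4, on the ingested palmitate tracer, gives the formula: "The FAO rate will be determined by excess plasma 2 H times TBW". The same sentence adds that "percent recovery of deuterium will be determined by dividing by dose of" the deuterium given. Sampling is frequent: "FAO will be quantified thereafter by hourly assessment of deuterium incorporation into plasma" water. The stated purpose is comparison between visits: "we use a validated technique to quantify differences in FAO between studies".

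The tracer is a single oral dose with dinner (sections 4 and 6a), and dinner is fixed: "At 5:30 PM, they will eat a standard dinner". The first blood sample, just before dinner, is the pre-isotope baseline.

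Two other places rely on FAO as a rate. Section 7b lists among the secondary outcomes "rate of lipolysis and FFA turnover using stable isotope data; rate of fatty acid oxidation". The data analysis part of section 4 makes a within-night prediction, "we predict that on CPAP, sleep reduces lipolysis and FAO compared to wakefulness", and a between-condition one, that OSA will lower FAO or leave it unchanged.

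The SAP's secondary metabolic outcomes are FFA, glucose and insulin; FAO is not among them.

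**The concern.** Deuterium released by oxidation collects in body water. Excess deuterium at a given time, multiplied by total body water (TBW), is therefore everything released since the baseline sample. Neither document includes a step that subtracts successive samples or divides by elapsed time.

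Two uses of FAO are affected. A running total rises for as long as any tracer is being oxidised, so the direction of a sleep-versus-wake comparison made on it is set by the clock. The protocol also reads FAO beside lipolysis, looking for more lipolysis without more oxidation. Section 4 measures FFA appearance in four separate one-hour windows, so that reading would set a window-specific rate against a total since dinner.

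**Working it through.** The documents give no numerical result, sample size or power for FAO, so there is no figure to reproduce. The check is one of dimensions and time windows.

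**Inputs (protocol section 4).** Hours are counted from the 5:30 PM dinner dose: sleep study start at 10:30 PM is t = 5, its end at 6:30 AM is t = 13, and the last sample at 9:00 AM is t = 15.5. Study drug follows a 6:30 PM blood pressure check (t about 1.0); section 6a gives 7:00 PM (t = 1.5).

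**1. Dimensions.** Let C(t) = excess deuterium(t) × TBW. Concentration times pool size is an amount. Dividing C(t) by the dose gives the percent recovered, as the protocol itself says; a rate divided by dose would be percent per hour. Ignoring the small loss of body water over 15.5 h, C(t) is the tracer oxidised from dinner to t. The rate over an interval is [C(t2) − C(t1)] / (t2 − t1).

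**2. Sleep versus wake.** Assume oxidation of 1 unit per hour before sleep and f units per hour during sleep. Then C(5) = 5 and C(13) = 5 + 8f.

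| | f = 1 | f = 0.7 | f = 0.5 |
|---|---|---|---|
| C at 10:30 PM | 5.0 | 5.0 | 5.0 |
| C at 6:30 AM | 13.0 | 10.6 | 9.0 |
| Change in C | +160% | +112% | +80% |
| Interval rate, [C(13) − C(5)]/8 | 1.00 | 0.70 | 0.50 |

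The level rises in every column; the increment recovers the true rate.

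**3. Between nights.** Compare a night with f = 1 and a night with f = 0.7, both returning to 1 unit per hour after 6:30 AM.

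- C at 6:30 AM: 13.0 − 10.6 = 2.4 units; 2.4/13.0 = 18.5%.
- C at 9:00 AM: 15.5 − 13.1 = 2.4 units; 2.4/15.5 = 15.5%.
- Sleep increment: 8.0 − 5.6 = 2.4 units; 2.4/8.0 = 30%.

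The absolute difference is the same three times. Only the percentage shrinks, because the sleep share of C is 8/13 = 62% at 6:30 AM and 8/15.5 = 52% at 9:00 AM. With an assumed rise-and-fall curve after the meal, (t/τ)·exp(1 − t/τ) peaking at τ = 4, 6 or 8 h, a 30% sleep effect reads as 17.2%, 20.4% or 21.9% at 6:30 AM.

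**4. Drug.** Tracer time before dosing is at most 1.5/13 = 12% of the 6:30 AM window and at least 1.0/15.5 = 6% of the 9:00 AM window.

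**5. Noise.** Suppose night-to-night variation is independent between evening and sleep, with assumed CVs of 10–30% and 10–20%. The standardised effect from C relative to that from the increment is 8·CVs / √[(5·CVe)² + (8·CVs)²], where CVe is for evening and CVs for sleep. At 20% for both this is 1.6/√(1.00 + 2.56) = 0.85; over the whole range it is 0.47 to 0.95.

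**6. Limits of the increment.** With no true sleep effect, the three curves in step 3 give a sleep-to-evening rate ratio of 0.84, 1.33 and 1.69. Absorption and tracer availability alone can thus mimic or hide a change with sleep.

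**The case against.** The strongest reply is that the method is presented as a comparison between visits, and cumulative recovery at a matched time serves that purpose. This stands. The planned tests for once-per-visit measures (paired t-tests in section 7c, one-way ANOVA in section 4) work on differences in means, and those are not shrunk. The hourly samples also mean that interval rates can be derived later without new measurements; the fault lies in the formula, not in the data.

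A reader might infer that the definition dilutes any effect of OSA or of propranolol and so favours the hypothesis of unchanged FAO. The documents do not support that. Dilution arises only on a relative scale and only for effects confined to sleep, and for the drug the pre-dose share is about 6–12%. Nor can one say that OSA has no influence before lights-out: section 4 has participants off CPAP for two nights at home before each OSA night, so evening oxidation may already differ. A sleep-only increment would leave that difference out.

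The reply does not reach the sleep-versus-wake prediction or the outcome named as a rate. Neither is a between-visit total.

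**Conclusion.** The formula in section 4 yields a cumulative amount, not a rate. As written it does not deliver the section 7b outcome and cannot show the predicted fall in FAO during sleep: a true halving would still appear as an 80% rise between 10:30 PM and 6:30 AM, assuming constant evening oxidation. That the level rises does not depend on this assumption; the 80% does.

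Between nights, the cumulative value is usable at a matched time. Percentage differences confined to sleep are understated (30% reads as about 18% at 6:30 AM under constant oxidation), and evening variation may add noise; the size of that rests wholly on assumed CVs and independence.

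The consequence is limited. FAO is secondary in protocol section 7b, appears among the additional outcomes of interest in section 2, and is absent from the SAP. The primary analysis is unaffected.

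**What to change.** In protocol section 4:

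- Relabel excess deuterium times TBW as cumulative oxidation, and its ratio to dose as cumulative recovery.
- Define the FAO rate as the change in excess deuterium between two samples, times TBW, divided by the interval.
- Pre-specify the 10:30 PM to 6:30 AM increment, with the 5:30 to 10:30 PM and 6:30 to 9:00 AM increments beside it, and compare the same clock interval between conditions. Showing the evening increment keeps any effect of the earlier nights off CPAP visible.
- State that a within-night sleep-versus-wake contrast remains confounded by absorption and tracer availability after a single oral dose.

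The cost is wording and a subtraction. An hourly series from 5:30 PM includes 10:30 PM and 6:30 AM; the 9:00 AM sample is drawn anyway but falls between hourly points, so its deuterium assay should be confirmed. The downside is more assay noise in short intervals, which the 8-hour increment largely avoids.

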**Study overview:** There are a total of 4 study visits. The first visit is a consent, screening, and randomization visit. After consent, a screening EKG will be performed to exclude rhythm or conduction abnormalities and a urine pregnancy test to exclude pregnancy in potentially pregnant females. (If the participant has had a clinical EKG or EKG report in the last year that does not indicate any conduction disorders listed in the exclusion criteria, the screening EKG may be deferred.) A point of care screening test for hemoglobin will also be performed to exclude pre-existing anemia. Patients with a hemoglobin < 10 g/dL are ineligible for this study. They will be provided with ClearPassage® NDS to use at home during CPAP withdrawal nights.

Thereafter, there are 3 overnight visits to the CRU in random order. This protocol compares nocturnal metabolism in treated OSA (CPAP), untreated OSA (NDS), and beta-blocked OSA (NDS) in the same subject. OSA nights are performed in the lab after using NDS instead of CPAP for 2 nights at home.

**Covid-19 screening:** We will screen participants before their arrival for their each sleep study with a Covid-19 test. A negative screen within 72 hours of the CPAP visit will be needed prior to admission for the CPAP study visit.

During each OSA visit, propranolol or placebo is taken in the evening, in random order. Frequent blood sampling is performed throughout the visit. In the morning, DEXA (only 1 DEXA needed for entire study) is performed. We are targeting 1 week between visits, but will allow flexibility in scheduling patients unable to schedule 3 consecutive visits exactly 1 week apart; in this scenario we will allow a duration of  $\geq$  4 days or  $\leq$  3 weeks between visits. Each visit we will also administer stable isotopes to measure detailed lipid metabolism.

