**b. Study duration and number of study visits required of research participants.**

Each subject will undergo 3 sleep studies spaced one week apart. Including the baseline consent/screening/randomization visit, there are a total of 4 study visits. Since visits are 1 week apart, the duration of involvement will be ~3 weeks. In the event that participants are not available to make visits exactly 1 week apart, we will allow visits to be spaced apart by  $\geq$  4 days and  $\leq$  3 weeks. Therefore, the minimum duration in the study is about 2 weeks, and the maximum time is 6 weeks.

If participants agree to being contacted for the ancillary calorimetry experiments, the time frame will be at least 1 week following completion of the PROSAT protocol. Participants will undergo 2 visits to the NIH (1 week apart) and under conditions of CPAP or NDS (CPAP withdrawal).

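### The FAO calculation has no stated rule for deuterium left over from earlier visits, and no visit term to absorb the resulting drift

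*Protocol*

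**What the plan says.** Protocol section 4, Study overview, on tracer dosing: "Each visit we will also administer stable isotopes to measure detailed lipid metabolism". Under Ingestion of [2H31]palmitate, the method is described as "providing an oral liquid dose of 15 mg/kg body mass of" deuterated palmitate, taken with dinner. On measurement: "FAO will be quantified thereafter by hourly assessment of deuterium incorporation into plasma" water. On the calculation: "The FAO rate will be determined by excess plasma 2 H times TBW". The reference value that defines the excess is not written out.

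The blood sampling paragraph names one candidate: "The first blood sample is taken at 5:30 PM, just before dinner and serves as a pre-medication, pre-isotope baseline". It also fixes the end of the window: "The final sample is obtained at 9:00 AM".

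On spacing, section 4b says "Each subject will undergo 3 sleep studies spaced one week apart", and the Study overview says "We are targeting 1 week between visits, but will allow flexibility in scheduling", with 4 days to 3 weeks allowed. Post-test procedures permits a repeat night at least 1 week after an inadequate one.

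On visit order, the Study overview puts the three overnight visits in random order. Pre-sleep procedures places the drug–placebo crossover on the second and third study nights.

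On analysis, Data Analysis and Anticipated Outcomes and section 7 describe mixed models with condition fixed and subject random, plus paired t-tests and one-way ANOVA. None has a visit or period term, and none is assigned specifically to FAO. FAO is a secondary outcome in protocol section 7 and is absent from the SAP's outcome list.

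**The concern.** The method works because label from oxidised palmitate collects in body water. Body water turns over across days, so one visit's label need not be gone by the next. The 5:30 PM sample is literally pre-isotope only at visit 1.

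A fresh pre-dose sample at each visit deals with the residual level. It does not deal with what that residual does over the following 15.5 hours. If it falls and the 5:30 PM value is held fixed, too much is subtracted by morning. The error is zero at visit 1, present at visit 2, larger at visit 3, and larger when visits are close together.

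The protocol uses this method to compare FAO between nights, so an error tied to visit number goes directly into the comparison. The consequence depends on visit order, on which the protocol makes two statements that do not sit together. The stated hypothesis is that OSA leaves FAO lower or unchanged, so an artefact that lowers later visits would favour it if CPAP always came first.

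**Working it through.** The plan gives no residual enrichment, turnover rate, expected recovery or tracer washout, so there is no figure of its own to reproduce.

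**Inputs from the protocol.** Window T = 15.5 h (5:30 PM to 9:00 AM) = 0.646 day. Gap G = 7 days (target), 4 days or 21 days (limits). The dose cancels out of the relative error.

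**Assumptions, not in the documents.** Body-water half-life 5–14 days, k = ln 2 / half-life. m = label from one visit that ends up in body water, divided by that visit's overnight signal, taken as 1–2. The 5:30 PM value is held fixed overnight.

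**Formulas.**
- Residual at visit 2, in units of one night's signal: m·exp(−k(G−T))
- Residual at visit 3: m·[exp(−k(G−T)) + exp(−k(2G−T))]
- Overnight fall: 1 − exp(−kT)
- Under-reading = residual × overnight fall

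**Example: half-life 7 days, G = 7, m = 1.** k = 0.099/day. Overnight fall = 1 − exp(−0.064) = 6.2%. Residual is 0.53 at visit 2 and 0.53 + 0.27 = 0.80 at visit 3. Under-reading is 0.53 × 6.2% = 3.3% at visit 2 and 0.80 × 6.2% = 5.0% at visit 3.

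**Range over half-life 5–14 days and m = 1–2:**

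| Gap | Visit 2 | Visit 3 |
|---|---|---|
| 4 days | 2.7–10.8% | 4.9–16.9% |
| 7 days | 2.3–7.1% | 3.9–9.9% |
| 21 days | 0.5–2.3% | 0.5–3.1% |

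**If much more label reaches body water after the visit.** Take k = 0.10/day, 50% of the dose eventually in body water and 10% recovered by 9:00 AM (a ratio of 5), with 7-day gaps. Residuals are 0.5·exp(−0.7) = 0.248 and 0.248 + 0.5·exp(−1.4) = 0.372 of a dose. The overnight fall is 6.25%, so the losses are 1.55% and 2.32% of dose. Divided by 10%, that is 16% and 23%. If overnight turnover runs at half the daily rate, the fall is 3.2% and the visit 2 error is 7.9%.

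**Late oxidation of stored label.** A two-pool model lets earlier label keep entering body water: W(t) = Σ R·a/(a−k)·[exp(−kt) − exp(−at)], with pool size R and oxidation rate a. The visit 2 error is [W(G) − W(G+T)]/W(T); visit 3 adds the same term with 2G. Most settings still give under-reading. With 15% of the dose oxidised fast (2/day), 80% stored and oxidised at 3% per day, and a 14-day half-life, weekly visits give over-reading of 4.0% at visit 2 and 5.1% at visit 3.

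**Effect on contrasts (half-life 7 days, G = 7, m = 1).**
- All three nights randomised: every condition carries on average (0 + 3.3 + 5.0)/3 = 2.8%, which cancels in expectation.
- CPAP always first: CPAP carries 0 and the OSA nights average (3.3 + 5.0)/2, about 4.1%. At m = 2 this is 8.3%. Propranolol and placebo share visits 2 and 3 in random order and stay balanced in expectation.

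**The case against.** The strongest reply is that the documents show silence, not a wrong analysis. The fixed subtraction is inferred from the words excess and baseline. The protocol calls the technique validated and cites a source for it that may define the baseline rule. A pre-dose draw at every visit already removes the main carryover, leaving only overnight drift. All of this stands, and it is why the point concerns an unstated rule and a residual drift.

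The sign is also open. The larger 16–23% errors require 40% of the dose to be oxidised after the visit, and oxidation still running at the next visit works the other way: in that scenario, oxidising 4.8% per day of the remaining 50% cancels the visit 2 error. This stands too. Under-reading is likely, not established.

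A reader might infer that the FAO result is built to confirm the OSA hypothesis. The documents do not support that. Under the random order in the Study overview, CPAP falls late as often as early, and the error becomes order-related noise. Only the CPAP-first reading of Pre-sleep procedures gives a systematic bias, and only in CPAP versus OSA.

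Finally, FAO is one of many secondary outcomes in the protocol and is not in the SAP. That limits the importance of the point without removing it.

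**Conclusion.** The gap is real and modest. Tracer is given again at short intervals, the same-visit baseline is not label-free after visit 1, and neither the FAO calculation nor any stated model accounts for the change in residual label overnight. On the main assumptions the error is about 2–7% at visit 2 and 4–10% at visit 3 with weekly visits, reaching about 17% at visit 3 when both gaps are 4 days. These figures rest on an assumed half-life and an assumed ratio of eventual to overnight label. A higher ratio raises them; late oxidation lowers them and can change the sign.

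With three-way randomisation the consequence is extra order- and spacing-related variability in a small crossover. If CPAP is always night 1, it is a bias toward the hypothesised lower FAO in OSA. Propranolol versus placebo remains balanced in expectation either way. The primary outcomes in both documents and both sample sizes are untouched.

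**What to change.** 1. State the FAO baseline rule, including which sample defines the excess at visits 2 and 3.
2. Analyse FAO in a mixed model with condition and visit number as fixed effects and subject as a random effect, instead of condition alone. This works whichever way the drift runs. It removes the average visit effect, not the part due to unequal gaps.
3. As a sensitivity analysis, recompute FAO with a declining baseline: visit 1's 5:30 PM value as the natural-abundance reference, and the later residual projected forward as residual × exp(−λt), with λ at 50–100% of the between-visit turnover rate. This should not be the main analysis. In the ratio-of-5 scenario with overnight turnover at half the daily rate, applying the whole-day rate would turn a 7.9% under-read into a 7.6% over-read.
4. Reconcile the Study overview with Pre-sleep procedures on visit order. If CPAP is always first, a visit term cannot separate CPAP from visit 1, and the CPAP contrast for FAO should be reported with that limitation.
5. Say whether a repeated night includes tracer, since that would add a further dose.

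The cost is two degrees of freedom, some analysis wording, and an assumed turnover range in the sensitivity analysis. No new visits or blood draws are needed.
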